5.5 Use of radiation: N/A

5.6 Use of Center for Magnetic Resonance Research: N/A

## 6.0 Data and Specimen Banking

6.1 Storage and Access: *All participants will receive a unique numerical ID which will be used in lieu of identifiable information whenever possible. All source data containing identifiers will be stored in locked cabinets in locked*

PROTOCOL TITLE:

VERSION DATE:

*rooms. All digital identifiable data will be stored on access-controlled, password-protected databases.*

6.2 Data: *Deidentified Neuroimaging data (EEG recordings) will be the only data stored*

## **7.0 Sharing of Results with Participants**

7.1 *Results of the study will not be shared with participants. The findings of the study will be shared via publication or presentation at a conference once all data has been collected/analyzed.*

## **8.0 Study Population**

8.1 Inclusion Criteria: *Participants will be recruited from the University and surrounding community. No vulnerable populations will be recruited for this study. Specific inclusion criteria are listed below:*

- *Between 18-50 years old*
- *Normal hearing ability*
- *No psychiatric medication prescription*
- *No clinically significant head injury or neurological disease*
- *No drug dependence past 6 months or no substance abuse in the past month*
- *Sufficient spoken English to understand study procedures*
- *Ability to give informed consent*

8.2 Exclusion Criteria: *Exclusion criteria are listed below:*

- *History or tDCS or other cortical energy exposure within past 12 months*
- *History of seizures or epilepsy*
- *Cranial metallic plates/screws*
- *Implanted devices*
- *History of craniotomy*
- *History of eczema on scalp*
- *Bipolar disorder or Depression diagnosis*
- *Cornrows or dreadlocked hair*
- *Impaired hearing*

8.3 Screening: *The screening process will happen over email or phone (depending on how participant makes contact). Potential participants will*

PROTOCOL TITLE:

VERSION DATE:

*be provided with information about the study using an established script and will be asked a series Health & Biological/Medical Application Form 7 of questions to determine if they meet basic inclusion/exclusion criteria.*

*They will be told about the basic aims of the study, and those interested in participating will be scheduled for the study. At the study visit, the participants will first complete the informed consent process*

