### **4.0 Study Intervention(s)/Investigational Agent(s)**

- 4.1 Description: *Transcranial Direct Current Stimulation (tDCS) is a noninvasive method of neuromodulation which applies low levels of electrical current to the scalp. TDCS can modulate plasticity and has been used for a variety of clinical and research purposes. We will apply tDCS bilaterally to the auditory cortex.*
- 4.2 Drug/Device Handling: *We will be using the StarStim8 (Neuroelectrics) device for tDCS and EEG recording. This device has been approved for use in research without an investigational device exemption due to meeting criteria for non- significant risk (NSR). In addition, the device has built in safety mechanisms which allow for the immediate cessation of stimulation should the subject become uncomfortable or if the impedance of the stimulation electrodes is too high. Stimulating electrodes will be placed over the auditory cortex and return electrodes will be placed over the supraorbital bone. 1 mA of current will be delivered for the duration of*

PROTOCOL TITLE:

VERSION DATE:

*stimulation. The device will be stored in a locked cabinet in our lab space. Our lab space on the 5th floor of the secure [name]. Only trained team members who are on the IRB protocol will have access to the locked cabinet.*

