*States without an investigational device exemption due to meeting criteria for non-significant risk. The device utilizes standard Ag/Cl electrodes embedded in an easy to use neoprene cap. A small amount of conductive gel is applied to each electrode before insertion into the head cap. Electrodes will be positioned on the subject's scalp according to the international 10/20 electrode placement system. During EEG recording, all electrodes will be utilized to record brain signal. The session will begin with EEG recording while the participant engages in a visual search task. Immediately after, either a passive Auditory Oddball paradigm or a passive Visual Oddball paradigm (these tasks are described in detail in the instruments section) will begin. They will be seated in front of a monitor as they observe visual stimuli or will be wearing insert headphones through which auditory stimuli will be delivered. After the first Oddball task, simultaneous EEG and tDCS will commence for a period of 10 min. During simultaneous EEG and tDCS, two electrodes will be used to deliver stimulation, while the remaining electrodes continue to record EEG. The two stimulation electrodes will be positioned bilaterally over the auditory cortex (T3/T4). In the anodal group the device will deliver 1mA of current through each stimulating electrode. The current is initiated in a ramp like fashion over a 10 sec period from 0mA to 1mA. Once at 1mA, the current is held constant for the duration of the session. Should the participant not be able to tolerate a current of 1mA due to pain or irritation, the current will be decreased down to a minimum of 0.5mA. If 0.5 mA is still not tolerable, the participant will be removed from the study. The sham procedure involves only 40 sec stimulation at 1mA and then drops to 0mA with 15ms pulses every 550ms. This simulates the tingling sensations that are often associated with active stimulation. 15min into the stimulation session the sensory tetanus will commence. The auditory tetanus involves the presentation of a 1000Hz tone at a rate of 13Hz for a period of approximately 5min. The visual tetanus involves the presentation of the visual stimulus (either a horizontal or vertical grating) at a rate of 9Hz. Sensory tetanus and tDCS will end at the same time. Briefly after tetanus and tDCS, the participants will perform the second oddball task as well as a final visual search task. 30 min after the cessation of tDCS, a final oddball task will be conducted. After the completion of the EEG recording, the head cap will be removed and the participant will be given the opportunity to wash their hair (towels and shampoo provided). The two study sessions will be identical, differing only in type of tDCS applied (sham or active).*

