
- Precautions Taken: *tDCS is considered to be a safe brain stimulation technique that rarely result in adverse events. There is currently no evidence of serious side-effects. We will discontinue any participant who experiences sores at the tDCS administration site, headaches that*

PROTOCOL TITLE:

VERSION DATE:

*impair global functioning, and worsening psychosis. Mild side-effects typically resolve upon discontinuation tDCS. The participant may choose to discontinue stimulation at any time during the session if experiencing discomfort or side effects. No other risks are anticipated. Nonetheless, in order to minimize risks, study staff will be using standards of administration that have been shown to be safe in numerous other studies and across more than 2000 studies (Liebetanz et al., 2009; Nitsche et al., 2007; Poreisz, Boros, Antal, & Paulus, 2007) using tDCS; this includes length of administration, magnitude of the current, size of electrode sponges used, and method of applying stimulation. Any unanticipated problems or adverse events will be reported according the University of Minnesota IRB standard operating procedure. 2. Participants will be informed that they are not required to answer any questions or participate in any activities which make them uncomfortable. 3. The results of this study may be published or presented but the participant's identity and records will not be revealed unless required by Federal Law. A Federal Law allows the U.S. Food and Drug Administration, Office for Human Research Protections, Government Accountability Office and other Federal agencies, the Research and Development Committee, representatives of USAMRMC, Henry M. Jackson Foundation, the University of Health & Biological/Medical Application Form 11 Minnesota Institutional Review Board (IRB), and/or the Institutional Review Board (IRB)/Human Studies Subcommittee of the VA Medical Center to review records. Because of the need for these inspections, absolute confidentiality cannot be guaranteed. However, every effort would be made to minimize these risks by providing the participant with a unique numerical identifier at the beginning of the study in order to protect their actual identification and maintain complete confidentiality.*

5.3 Study Duration: *We plan on enrolling participants through May 2019. Data analysis should be completed by December 2019.*

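### The skin exclusion in 8.2 names only the scalp, while 4.2 places return electrodes on the forehead: a minor participant-safety mismatch that depends on which montage is used

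*Combined protocol and SAP*

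**What the plan says.** The only criterion about skin in the two eligibility lists is in 8.2: "History of eczema on scalp". Section 8.1 lists none.

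On electrode sites, the protocol says three things:

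- Section 4.1 describes tDCS in general as a method that "applies low levels of electrical current to the scalp".
- Section 4.2 gives the montage: "Stimulating electrodes will be placed over the auditory cortex and return electrodes will be placed over the supraorbital bone".
- Section 5.2 says "Electrodes will be positioned on the subject's scalp according to the international 10/20 electrode placement system". It adds that during stimulation "two electrodes will be used to deliver stimulation, while the remaining electrodes continue to record EEG", and puts those two at T3/T4. It mentions no return electrode.

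On skin harm, the precautions in 5.2 state: "We will discontinue any participant who experiences sores at the tDCS administration site". Section 13.1 repeats sores at the site among the rare reasons for discontinuation.

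Screening (5.2 and 8.3) consists of scripted questions by email or phone on the basic eligibility criteria. No skin inspection is described.

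**The concern.** An exclusion for eczema in a stimulation study is most naturally read as protecting vulnerable skin from current. To do that, it has to cover every site where current enters or leaves the body. Return electrodes complete the circuit, so between them they carry the same total current as the stimulating electrodes. If they sit on the forehead, as 4.2 says, a criterion limited to the scalp leaves one set of current sites uncovered.

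What is at stake is an avoidable skin exposure in healthy volunteers. Section 14.1 tells them to expect no benefit, and under 19.1 the cost of care for a research injury is not met by the study. A protocol that already names both the skin condition and the skin harm should apply the first to all the sites where the second could occur.

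**Working it through.** The protocol states no figure on this point and no formula applies. The check is to set the sections side by side.

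1. **Sites covered by the skin exclusion.** From 8.2: the scalp. From 8.1: none.

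2. **Sites that carry current under 4.2.** Scalp over the auditory cortex (stimulating electrodes) and skin over the supraorbital bone, that is, the forehead (return electrodes).

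3. **Difference.** The sites in step 2 less the site in step 1 leave the forehead skin under the return electrodes.

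4. **Does another criterion close the gap before exposure?** No other item in 8.1 or 8.2 names a skin condition or a skin site. Screening is remote, and 11.2 says that medical records are not collected. A volunteer asked whether they have had eczema on the scalp can truthfully say no while having it on the forehead.

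5. **Does another provision close it later?** Several limit the harm, but all act once stimulation is under way or being attempted:
   - the device's built-in cut-off for discomfort or high impedance (4.2);
   - reduction of current, or removal, for pain or irritation (5.2);
   - the participant's freedom to stop (5.2);
   - discontinuation for sores (5.2 and 13.1).

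   None prevents the first exposure.

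6. **Same comparison under 5.2.** Two electrodes at T3/T4 deliver stimulation and the rest record. Both stimulation sites are on the scalp, so the difference in step 3 is empty and the gap does not arise.

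The result therefore depends on the montage. Under 4.2 the exclusion misses a current site, and under 5.2 as written it does not. The two sections disagree, and nothing in the protocol says which governs.

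**The case against.** Four objections deserve an answer.

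*The protocol uses the word scalp for electrode sites in general.* It does so in the background (2.1), in 4.1 and in 5.2. The authors may have meant eczema wherever an electrode goes. This stands as an account of intent, and it makes the point one of wording. It does not settle the matter, because the criterion is applied by putting a question to a lay volunteer, who would not ordinarily count the forehead as scalp.

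*The forehead site appears only in 4.2.* This also stands. The disagreement between 4.2 and 5.2 is the more basic defect, and the eczema gap follows from one side of it. A reader might take the 4.2 montage as settled, but the documents do not allow that.

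*The screening script is not reproduced.* Staff may already ask about skin under all electrodes. It can be said that the criteria do not exclude such a person, but not that such a person will in fact be enrolled.

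*Later safeguards limit the harm.* They do, and 13.1 calls discontinuation events rare. No section links eczema to sores. This lowers the weight of the point without removing the mismatch.

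A reader might also infer a statistical cost: a skin reaction removes a pair from the within-participant contrast, lowers power, and does so mostly in the active session. The documents do not support this. Section 10.1 sets a target of 35 completers and a ceiling of 80 consents, which leaves 80 − 35 = 45 further consents from which a lost participant could be replaced. Nor does the protocol say that skin reactions would fall mainly in the active session. Under 5.2 the sham also delivers 1 mA, for 40 seconds, followed by brief pulses.

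**Conclusion.** The point holds as a minor participant-safety mismatch. As written, 8.2 does not exclude a person with eczema confined to the forehead, and under the 4.2 montage that person could receive current through the affected skin.

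The conclusion rests on two assumptions: that 4.2 describes the montage to be used, and that scalp in 8.2 is read in its ordinary sense. If either fails, the gap closes.

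The number affected cannot be derived from the documents. If 0 to 2 among 35 completers is assumed, the range includes none. No effect on power, sample size, attrition or the primary analysis is claimed.

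**What to change.** First, reconcile 4.2 with 5.2, so that the protocol states once which electrodes carry current, stimulating and return, and where each sits. Which montage is correct is for the investigators to say.

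Then reword the existing eczema exclusion in 8.2 so that it refers to any skin site where a current-carrying electrode will be placed under that montage, and align the question in the email and phone script with it. Defining the criterion by electrode site means that it stays correct whichever montage is confirmed.

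The cost is one line in 8.2 and one screening question. The downside is that a very small number of otherwise eligible volunteers would be excluded. If the reconciled montage has no electrode off the scalp, the rewording excludes nobody beyond those excluded now.

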## **9.0 Vulnerable Populations**

### 9.1 Vulnerable Populations:

- Children
- Pregnant women/Fetuses/Neonates
- Prisoners
- Adults lacking capacity to consent and/or adults with diminished capacity to consent, including, but not limited to, those with acute medical conditions, psychiatric disorders, neurologic disorders, developmental disorders, and behavioral disorders
- Approached for participation in research during a stressful situation such as emergency room setting, childbirth (labor), etc.
- Disadvantaged in the distribution of social goods and services such as income, housing, or healthcare
- Serious health condition for which there are no satisfactory standard treatments
- Fear of negative consequences for not participating in the research (e.g. institutionalization, deportation, disclosure of stigmatizing behavior)
- Any other circumstance/dynamic that could increase vulnerability to coercion or exploitation that might influence consent to research or decision to continue in research
- Undervalued or disenfranchised social group
- Members of the military
- Non-English speakers
- Those unable to read (illiterate)
- Employees of the researcher
- Students of the researcher
- None of the above

### 9.2 Additional Safeguards: N/A

## **10.0 Local Number of Participants**

### 10.1 Local Number of Participants to be Consented: *Up to 80 participants will be consented for the study. The goal is to have 35 complete the study.*

## **11.0 Local Recruitment Methods**

PROTOCOL TITLE:

VERSION DATE:

- 11.1 Recruitment Process: *Recruitment will be conducted using posted flyers as well as ads posted on Craigslist. Flyers will be posted around campus both outside and inside buildings. Ads will be placed on Craigslist under "part time gigs".*
- 11.2 Identification of Potential Participants: *Interested participants will get in contact with study staff using email or phone calls. Initial contact will be made primarily by the student investigator. No medical records will be asked for/collected as a part of this study.*
- 11.3 Recruitment Materials: *Recruitment materials include posted flyers and ads on craigslist.*
- 11.4 Payment: *We will use the Greenphire ClinCard System to pay our participants. Participants will receive the card with \$20 preloaded at the end of the first study session. \$20 more will be loaded onto the card at the completion of the second study session. Research experience points may also be awarded*

## **12.0 Withdrawal of Participants**

- 12.1 Withdrawal Circumstances: *If we cannot collect quality EEG data from the subject due to the following reasons, the participant will be withdrawn from the study*
  - *Excessively thick hair*
  - *Small earlobe (cannot place earclip electrode)*
  - *Excessive movement during EEG*
  - *Excessive blinking during EEG*
  - *Issues with lack of alertness (falling asleep)*
- 12.2 Withdrawal Procedures: *In the case that a participant withdraws, the PI will be notified and data collection from that subject will immediately cease. Records will be updated to reflect a withdrawal. No partial withdrawal option is given for this study.*
- 12.3 Termination Procedures: N/A

## **13.0 Risks to Participants**

- 13.1 Foreseeable Risks: *There is currently no evidence of serious side-effects associated with tDCS. Criteria for discontinuation that may rarely occur are sores at the tCS administration site, headaches that impair global functioning, and worsening psychosis. Mild side-effects that typically resolve upon discontinuation tDCS include light itching under the electrode at the beginning of administration, headache, fatigue, and nausea.*
- 13.2 Reproduction Risks: N/A

PROTOCOL TITLE:

VERSION DATE:

13.3 Risks to Others: **N/A**

## **14.0 Potential Benefits to Participants**

14.1 Potential Benefits: *No benefits expected for participating in the study*

## **15.0 Statistical Considerations**

15.1 Data Analysis Plan: *Data analyses will include traditional statistical analyses for within-groups differences in EEG neuroimaging data.*

15.2 Power Analysis: *35 participants in a within-groups design will provide the statistical power ( $1 - \beta = 0.80$ ) necessary to detect effect sizes greater than  $d' = 0.450$ . Based on the large effect sizes ( $d' > 0.68$ ) reported by Clapp et al. (2005) we expect to be sufficiently powered with the aforementioned sample size.*

15.3 Statistical Analysis: *Data will be analyzed in a 2-way ANOVA with correction for multiple comparisons*

15.4 Data Integrity: *EEG data will be subjected to standard quality control measures (both automated and manual) including measuring and controlling for artefacts.*

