**Hypothesis: Anodal tDCS will enhance the induction of LTP (as measured by potentiation of AEP's) compared to Sham.**

## 2.0 Background

- 2.1 Significance of Research Question/Purpose: *Experience dependent plasticity is generally defined as the ability of a nervous system to dynamically shift functional or structural states in response to extrinsic and intrinsic factors. Research over the past 50 years demonstrates that experience dependent plasticity is a fundamental property of the brain and is critical for everyday functioning. It allows us to learn and recall patterns, predict and obtain reward, and guides response selection for adaptive behavior (Cooke and Bliss, 2006; Ganguly and Poo, 2013). Given its fundamental role in brain dynamics, maladaptive experience dependent plasticity can lead to debilitating conditions. Disrupted synaptic plasticity is thought to play a significant role in the pathophysiology of several severe psychiatric disorders, including schizophrenia (SZ), bipolar disorder and major depressive disorder (Elvsåshagen et al., 2012; Normann et al., 2007; Stephan et al., 2006). The contribution of disrupted plasticity is most clearly*

PROTOCOL TITLE:

VERSION DATE:

*implicated in SZ, a serious neuropsychiatric illness that impacts 1% of the population and presents with a host of positive, negative and cognitive symptoms. Therefore, treatments that can assess or even enhance plasticity have the potential to be of great clinical value.*

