4.3 Biosafety: N/A

4.4 Stem Cells: N/A

## 5.0 Procedures Involved

5.1 Study Design: *The study will be conducted in a blinded, within-groups design involving two separate study sessions. The two sessions will consist of simultaneous tDCS and EEG recording. Each participant will receive both active and sham tDCS over the course of the two sessions (but not within a single session). Order of stimulation type will be counterbalanced across participants. The two sessions will be spaced at least 24 hours apart. The consent process will be done at the first study session. The primary outcome measure will be the difference in the amplitude of the ERP's (specifically the N100 component) recorded before and after tDCS. This difference is reflective of the capacity of the sensory cortex to support synaptic plasticity.*

5.2 Study Procedures:

- Screening Visit: *The screening process will happen over email or phone (depending on how participant makes contact). Potential participants will be provided with information about the study using an established script and will be asked a series of questions to determine if they meet basic inclusion/exclusion criteria (see below). They will be told about the basic aims of the study, and those interested in participating will be scheduled for the study.*
- Study visits: *Visits will take place at our [name] offices, the Ambulatory Research Center (ARC) at the department of Psychiatry, or at the clinical spaces at our St. Louis Park location. At the first study session, the participants will complete the informed consent process. The participant will also be told that this is not a treatment study and no benefits to the participant are expected from the study. After, and if, they complete the process, the participant will fill out the tDCS Side Effect Questionnaire (TSEQ), and the Edinburgh Handedness Inventory. These two brief questionnaires ask about potential side-effects of tDCS and the subject's handedness respectively. After the paperwork has been completed, the participant will undergo EEG and either active or sham tDCS (see embedded figure). The stimulation and the recording will be provided using the StarStim Neurostimulator (Neuroelectrics, Inc.). This device has been approved for use in research in the United*

PROTOCOL TITLE:

VERSION DATE:

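### The 2-way ANOVA states no session or order term for a counterbalanced two-session crossover, so a session effect on the N100 change would be left in the error

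*Combined protocol and SAP*

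**What the plan says.** Section 5.1 gives every participant active and sham tDCS in two separate sessions at least 24 hours apart, and adds: "Order of stimulation type will be counterbalanced across participants". Section 5.2 makes the sessions the same apart from the type of stimulation. The primary outcome in section 5.1 is the difference in N100 amplitude "recorded before and after tDCS". The hypothesis under Specific Aims is that "Anodal tDCS will enhance the induction of LTP" compared with sham.

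The model statement in section 15.3 is a single sentence: "Data will be analyzed in a 2-way ANOVA with correction for multiple comparisons". The two factors are not named. Section 15.1 adds only that within-groups differences will be analysed. No session, period, order or sequence term appears anywhere in the document.

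Section 5.2 has two oddball recordings after stimulation: "Briefly after tetanus and tDCS, the participants will perform the second oddball task", and "30 min after the cessation of tDCS, a final oddball task will be conducted". The plan does not say which of them is the after-tDCS value for the primary outcome.

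Section 10.1 sets the numbers: "Up to 80 participants will be consented for the study. The goal is to have 35 complete the study".

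**The concern.** Counterbalancing protects a crossover estimate from session effects on average, but it does not take their variation out of the error. That requires a term in the model. Given the hypothesis and the outcome, the natural 2-way ANOVA is stimulation (anodal, sham) by time (before, after), both within participant. If the N100 change tends to be larger or smaller in the second session, that shift raises the anodal-minus-sham difference in one order group and lowers it in the other. Without an order term, this spread is counted as noise.

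If the order groups also differ in size among completers, part of the shift moves into the estimate as bias. Thirty-five completers cannot split evenly. The document does not say when order is assigned, or whether participants who withdraw are replaced within order.

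**Working it through.** **Inputs from the documents.** 35 completers, d' = 0.450 and power 0.80 (section 15.2); up to 80 consented (section 10.1); two sessions with counterbalanced order (section 5.1).

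**Assumptions.** Alpha is not stated; 0.05 two-sided is used, because an ANOVA F test is non-directional. d' is taken in SDs of the anodal-minus-sham difference in N100 change. The session effect P is the session-2 minus session-1 difference in the N100 change, in the same SD units. The documents give no value for P, so 0.2 to 1 is an assumed range. One post-stimulation recording is used unless stated otherwise.

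**The plan's own figure.** A paired t-test with n = 35 and d' = 0.450 has power 0.73 two-sided and 0.83 one-sided. Neither reproduces 0.80. That is a separate matter; the comparisons below are made against the recomputed values.

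**Model.** For each participant let D = tau + sP + e, with s = +1 if anodal is given in session 2, s = -1 if in session 1, and SD(e) = 1.

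- *Without the term:* a one-sample t on D with 34 df, which equals stimulation by time in a 2x2 repeated-measures ANOVA.
- *With the term:* the average of the two order-group means with pooled within-order variance and 33 df. P cancels.

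Without the term, with n1 and n2 completers in the two orders:

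- bias = P(n1 - n2)/35 in absolute size
- expected sample variance of D = 1 + P² × 4·n1·n2/(35 × 34)

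At 18/17 and P = 0.5 the bias is 0.5 × 1/35 = 0.014. The variance is 1 + 0.25 × 1224/1190 = 1.257. The true effect of 0.450 is therefore judged against an SD of about 1.12 instead of 1.

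**Power at tau = 0.450, split 18/17, two-sided 0.05.** The extra participant can fall in either order, so both cases are shown.

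| P (assumed) | Without term, favourable | Without term, unfavourable | With term | Loss (points) |
|---|---|---|---|---|
| 0.2 | 0.732 | 0.710 | 0.733 | 0 to 2 |
| 0.3 | 0.721 | 0.687 | 0.733 | 1 to 5 |
| 0.5 | 0.680 | 0.620 | 0.733 | 5 to 11 |
| 1 | 0.482 | 0.356 | 0.733 | 25 to 38 |

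Two variations give the same picture:

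- If the test were one-sided, power at P = 0.5 would be 0.80/0.75, against 0.83 with the term.
- If both post recordings enter a 2x3 ANOVA (assuming independent, equal-variance errors and the same tau and P at both), power at P = 0.2 and 0.5 is 0.77/0.75 and 0.74/0.67, against 0.77 with the term.

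**Bias and two-sided type I error without the term.**

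| Split | Bias | P = 0.2 | P = 0.5 | P = 1 |
|---|---|---|---|---|
| 18/17 | 0.029P | 0.046 | 0.029 | 0.006 |
| 20/15 | 0.143P | 0.049 | 0.043 | 0.027 |
| 22/13 | 0.257P | 0.056 | 0.077 | 0.105 |

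With the term, type I error is 0.05 throughout.

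**How likely is imbalance?** Suppose N participants are assigned evenly to the two orders and 35 complete at random (hypergeometric). The chance of 20/15 or worse is 4.7%, 21.7% and 36.7% for N = 40, 50 and 80. The chance of 22/13 or worse is 0, 1.2% and 7.1%.

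**The case against.** **The factors are inferred.** Session or order could be one of the two factors, and then the term is already there. That cannot be ruled out from the text. Since section 5.2 offers auditory or visual tasks, modality could also be a factor, but a session effect would then still go unmodelled. What is certain is that no session or order term is stated.

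**The design already does most of the work.** The outcome is a within-session change, so a session shift that moves the before and after amplitudes equally cancels. Only a session effect on the change itself matters, and near balance it causes almost no bias. This is right, and it is why the point is minor.

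**The size is assumed.** A P of 0.5 already exceeds the detectable stimulation effect of 0.450, and P = 1 is more than twice it. The lower rows of the power table are the more believable ones to plan on: P = 0.2 to 0.3, with losses of 0 to 5 points.

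**The plan expects a larger effect.** At d' = 0.68, power without the term is 0.96/0.95 at P = 0.5, against 0.97 with it, so little would be lost. However, section 15.2 takes that figure from a study of potentiation by tetanus, and it need not carry over to an anodal-versus-sham contrast.

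**Severe imbalance is unlikely.** The 7.1% figure needs all 80 to be assigned an order. Some withdrawal reasons in section 12.1, such as hair thickness or earlobe size, could come to light when the cap is fitted. This stands: 22/13 is an extreme case.

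**The choice of post recording is a different issue.** It is, and it adds no weight here. It is mentioned because the same sentence of section 15.3 would settle it.

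**Conclusion.** The concern holds, as a minor point. Unless session or order is one of the two unnamed factors, a session effect on the N100 change stays in the error. At d' = 0.450 and an 18/17 split, the two-sided power loss is 0 to 2 points for a session effect of 0.2 SD, 1 to 5 for 0.3 SD and 5 to 11 for 0.5 SD. These sizes are assumptions, and with no session effect nothing is lost.

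Validity is not the main issue. Near balance the test is conservative, and two-sided type I error rises clearly above 5% only at splits of about 22/13. The case for change is that the order factor is already in the design and using it costs almost nothing.

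**What to change.** In section 15.3:

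1. Keep the repeated-measures ANOVA. Name stimulation and time as within-participant factors, and add order group as a between-participant factor with its interactions (equivalently, a session term in a model for the N100 change).
2. Estimate the stimulation effect on the N100 change as the equally weighted average of the two order groups, so that unequal completion does not bias it.
3. State which post-tDCS recording is primary or, if both are tested, that the planned multiple-comparison correction covers them.
4. Report the number of completers in each order.
5. State that the term does not remove carry-over that differs after active and after sham: a difference lambda between the two leaves a bias of lambda/2.

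The cost is a few lines of analysis text, one line of reporting and one degree of freedom. With no session effect, two-sided power at d' = 0.450 goes from 0.734 to 0.733 at 18/17, 0.725 at 20/15 and 0.704 at 22/13. Visits, stimulation and sample size are unchanged.
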